5.6 Concomitant Medications

Consistent with subject safety and comfort, administration of any prescription or over-the-counter drug products other than study medication should be minimized during the study period. Subjects should be discouraged from use of street drugs, herbal remedies, self-prescribed drugs, tobacco products, or excessive alcohol during the clinical study.

If considered necessary for the subject’s wellbeing, drugs for concomitant medical conditions or for symptom management may be given at the discretion of the investigator. The investigator’s decision to authorize the use of any drug other than study drug should take into account subject safety, the medical need, the potential for drug interactions, the possibility for masking symptoms of a more significant underlying event, and whether use of the drug will compromise the outcome or integrity of the study.

Subjects should be instructed about the importance of the need to inform the clinic staff of the use of any drugs or remedies (whether prescribed, over-the-counter, or illicit) before and during the course of the study.

Recommendations with regard to specific types of concomitant therapies, supportive care; diet and other interventions are as follows:

Concomitant medications are recommended as prophylaxis for nausea, vomiting, and infections, and are allowed for managing myelosuppression as shown in Table 3. Myelosuppression is expected in patients with AML due to underlying disease, as well as due to chemotherapy (such as 5-azacytidine), or both. Most patients have neutropenia, thrombocytopenia, or both at study entry. Significant or life-threatening myelosuppression may be managed with growth factor support and blood transfusion according to institutional standard of care, American Society of Clinical Oncology (ASCO) Practice Guidelines, and/or NCCN Practice Guidelines.

Infections secondary to myelosuppression are common in patients with AML, and may be related to underlying disease, chemotherapy, or both. Therefore, the use of prophylactic antibiotics, antifungal agents, and antiviral agents is recommended according to institutional standards.

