Since the effect of both avelumab and 5-azacytidine may be delayed, patients with high WBC counts may receive hydroxyurea prior to study entry. Hydroxyurea is allowed before the start of study therapy and during the study treatment. Hydroxyurea use would be recorded in the case report form (CRF). Concurrent therapy for CNS prophylaxis or continuation of therapy for controlled CNS disease is permitted. With the exception of these agents, concomitant systemic chemotherapy or radiation therapy is not permitted. Subjects are not allowed to participate concurrently in any other therapeutic clinical study.

Subjects may be receiving systemic corticosteroids (daily doses ≤ 10 mg of prednisone or equivalent if indicated for adrenal replacement or antiemetic therapy), topical, or inhaled corticosteroids at study enrollment. They may receive systemic, topical, inhaled, or enteric corticosteroids while on study without limitation if they develop conditions that require corticosteroid therapy; such subjects are not required to discontinue study participation.

All ongoing medications and therapies (including herbal products, nutritional supplements, and nontraditional medications) at screening will be considered prior medications. Concomitant medication data will not be collected or entered into the case report form other than hydroxyurea as mentioned above; however, the subject's medication record will contain a list of concomitant medications. If a prohibited medication is inadvertently administered/ taken by the patient, the patient may remain on study as long as the prohibited medication is discontinued as soon as feasible. If a prohibited medication is considered essential for the patient well being, continuation on study with concomitant administration of such medication(s) will need to be discussed with and approved by the principal investigator and medical monitor

Table 4: Instructions for the use of concomitant medications and therapies

Category of Use	Medication	Comment on Use	Restriction on Use
Recommended	Prophylactic antibiotics, antifungal agents, and antiviral agents	Strongly encouraged	None
	Antiemetic agents	According to standard of care at MDACC	None
Allowed	Oral allopurinol or rasburicase	At investigators discretion	None
	Leukapheresis	According to standard of care at MDACC	Before induction 1 day 1 only
	Red blood cell	None	None

Category of Use	Medication	Comment on Use	Restriction on Use
	transfusion		
	Platelet transfusion	None	None

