clinic visits for clinical evaluation and physical examinations. If the patient cannot make it to the MDACC clinic for this visit, the required follow up treatment procedures may be done with a local physician and the records forwarded to MDACC. The research nurse will contact the patient by telephone and get a verbal assessment of the patient's condition. The phone conversation will then be documented in the patient's charts.

^j Every 3-6 months for up to 5 years after last dose of study drug patient will have a physical exam and blood (about 1-2 teaspoons) will be drawn for routine testing. If the patient is unable to return to MD Anderson, they may be called by a member of the research staff and asked how they are feeling.

^k For patients that remain on study with no significant toxicity for more than 6 months, subsequent evaluations during study may be modified after discussion with the principal investigator. These include a decrease in frequency of bone marrow aspirations to every 6-12 months (or as clinically indicated), correlative studies to every 6-12 months (or suspension of sample collection for correlative studies), other laboratory tests to once every cycle.

^L [Perform at specified time-points and](#) repeat as clinically indicated

Data regarding adverse events will be collected during the study. Protocol specific data will be entered into PDMS/CORe. PDMS/CORe will be used as the electronic case report form for this protocol. While investigators do not need to report all adverse reactions, they must be recorded. The Principal Investigator will sign and date the AE log per each patient at the completion of each course. Following signature, the AE log will be used as source documentation for the adverse events for attribution.

Treatment may be discontinued for a variety of reasons, including patient withdrawal, investigator decision, and reasons specified by the protocol. Reasons for discontinuation of treatments are described in section 9.0.

8.0 CRITERIA FOR RESPONSE:

Response Criteria for AML

Responses will be assessed by the International Working Group for AML [67]. Responders are patients who obtain a CR, CRi, or PR, with or without cytogenetic response, hematologic improvements, and morphologic leukemia-free state.

Hematologic Improvement (HI): Hematologic response will be assessed by the MDS IWG response criteria (Cheson et al., Blood 2006)

- ◆ **Erythroid response (E)** (pretreatment Hgb <11 g/dL)
Hgb increase by ≥ 1.5 g/dL

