- ◆ **Platelet response (P)** (pretreatment platelets <100 x10⁹/L)
Absolute increase of ≥ 30 x 10⁹/L for patients starting with > 20 x 10⁹/L platelets
Increase from < 20 x 10⁹/L to > 20 x 10⁹/L and by at least 100%
- ◆ **Neutrophil response (N)** (pretreatment ANC <1.0 x10⁹/L)
At least 100% increase and an absolute increase > 0.5 x 10⁹/L
- ◆ **Blast response (B)**
 $\geq 50\%$ reduction in peripheral blood or bone marrow blasts but still >5%

8 DISCONTINUATION OF TREATMENT:

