11.1 Sample Size

Part a. Lead-in phase IB

The primary objective of the lead-in phase is to determine the MTD and DLT of avelumab in combination with 5-azacytidine in patients with refractory/ relapsed AML during the first cycle (28 days). 12 - 18 participants will be accrued into lead-in part of the study.

Once safety of the MTD has been established, any patients still on study at a dose lower than MTD can be dose escalated up to MTD.

Part b. Phase II

The primary objective of the phase II is to determine the efficacy of avelumab in combination with 5-azacytidine in patients with refractory/relapsed or untreated AML. The efficacy of the combination will be measured by the overall response rate (ORR), defined as CR (complete remission) + CR_p (complete remission with incomplete platelet recovery) + CR_i (complete remission with incomplete count recovery) + PR (partial response) + morphologic leukemia free state (MLFS)+HI within 3 months of treatment initiation among adult patients with refractory/ relapsed AML. ORR and toxicity will be monitored simultaneously using the Bayesian approach of Thall, Simon, Estey (1995, 1996) and the extension by Thall and Sung (1998).

Up to 40 additional patients (excluding patients treated at the MTD from the lead-in part) will be recruited for the Phase II part.

Total accrual: 12-18 patients from lead-in + 40 Phase II patients (N= 52 - 58 patients)

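### HI counts toward the primary ORR on printed thresholds with no confirmation or supportive-care condition, so transfusion, growth factors or hydroxyurea can create responders and weaken the futility rule

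*Combined protocol and SAP*

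**What the plan says.** Section 11.1 makes HI part of the phase II primary endpoint, whose list of components ends with "morphologic leukemia free state (MLFS)+HI within 3 months of treatment initiation among adult patients". Section 8.0 says the same of responders: "Responders are patients who obtain a CR, CRi, or PR, with or without cytogenetic response, hematologic improvements, and morphologic leukemia-free state".

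For HI, Section 8.0 cites an outside standard ("Hematologic response will be assessed by the MDS IWG response criteria") and then prints thresholds:

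- Erythroid, for pretreatment Hgb below 11 g/dL: "Hgb increase by ≥ 1.5 g/dL".
- Platelets, for pretreatment below 100: a rise of at least 30 from a start above 20, or from below 20 to above 20 with at least a doubling (all x 10⁹/L).
- Neutrophils, for pretreatment ANC below 1.0: at least a doubling and a rise of more than 0.5 (x 10⁹/L).
- Blasts: at least a 50% "reduction in peripheral blood or bone marrow blasts but still >5" percent.

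No duration, confirmatory value or condition on transfusion, growth factor or hydroxyurea is printed.

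Section 5.6 states: "Significant or life-threatening myelosuppression may be managed with growth factor support and blood transfusion according to institutional standard of care". Table 4 lists red cell, platelet and white cell transfusion, myeloid and platelet growth factors, and erythropoietin or darbepoetin as allowed, with no restriction. On cytoreduction: "Hydroxyurea is allowed before the start of study therapy and during the study treatment". On data capture: "Concomitant medication data will not be collected or entered into the case report form other than hydroxyurea as mentioned above". Other medications stay in the subject's medication record. The analysis plan in Section 11.2 has no rule for supportive care and no analysis of ORR without HI.

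**The concern.** Each printed HI threshold can be met by a measure that the protocol allows and that says nothing about the study drugs. Hgb going from 7.5 to 9.0 g/dL after red cells is a rise of 1.5. Platelets going from 10 to 22 after a platelet transfusion cross 20 and more than double. ANC going from 0.4 to 1.0 on growth factor is a rise of 0.6 and more than a doubling. Peripheral blasts going from 40% to 18% on hydroxyurea are a 55% fall and still above 5%, whatever the marrow shows. The blast case is the clearest, because the printed text accepts blood or marrow and Section 5.6 expressly allows hydroxyurea during treatment.

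Section 5.6 says that most patients enter with neutropenia, thrombocytopenia or both. Section 7.2.2 schedules counts twice weekly for three cycles, about 24 counts (2 x 4 x 3), so there are many occasions for a transient qualifying value.

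Two things are at stake: the ORR estimate, which is judged against 10% and 30%, and the Table 8 futility looks, which use the same responder count.

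**Working it through.** **Inputs.** From Sections 11.1 and 11.2: historical ORR 10%, target 30%, 40 phase II patients, response prior Beta(0.2, 1.8), looks every 5 patients from n = 5, stopping when Pr(ORR < 0.10 + 0.20 | data) > 0.975. Not in the documents and therefore assumed: q, the share of patients without a true response who meet an HI threshold only through supportive care.

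**Reproducing the plan.** With r responders among n, the posterior is Beta(0.2 + r, 1.8 + n − r). For example, Pr(ORR < 0.30) is 0.991 at 0/5 (stop) and 0.834 at 1/5 (continue); at n = 15 it is 0.9945 for 1 responder (stop) and 0.964 for 2 (continue). The maximum responder counts for stopping at n = 5, 10, …, 35 are 0, 0, 1, 2, 3, 4, 5, which is Table 8. Exact binomial recursion over these looks, combined with the toxicity bounds of Table 7 and with response and toxicity independent, gives all 25 cells of Table 9 to four decimals (at 10% toxicity: 0.9294 for ORR 10%, 0.2029 for ORR 30%). The design arithmetic is sound; the question is what goes into the responder count.

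**Effect of q.** With a true ORR of 10%, counted ORR = 0.10 + 0.90q. For q = 5%, 10% and 20%:

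- 0.10 + 0.90 x 0.05 = 0.145
- 0.10 + 0.90 x 0.10 = 0.19
- 0.10 + 0.90 x 0.20 = 0.28

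Passing these through the same rules:

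| Assumed q | Counted ORR | P(stop early), toxicity 10% | P(stop early), toxicity 30% | P(reach 40 with ≥ 12 responders), futility rule only |
|---|---|---|---|---|
| 0 | 10% | 0.93 | 0.93 | 0.0003 |
| 5% | 14.5% | 0.76 | 0.78 | 0.008 |
| 10% | 19% | 0.56 | 0.58 | 0.055 |
| 20% | 28% | 0.24 | 0.29 | 0.40 |
| 22.2% | 30% | 0.20 | 0.25 | 0.50 |

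The last row is where the whole gap closes: 0.20 / 0.90 = 22.2%. In 40 patients that is 4 true responders plus 8 of the other 36.

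**The other end of the range.** If the historical 10% was counted under the same rules and with the same supportive-care share, an inactive regimen would also show a counted ORR of 10%, and P(stop) would stay at 0.93. For a given q, the truth lies between 0.93 and the figure in the table.

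**The case against.** The strongest reply is that Section 8.0 incorporates the MDS IWG criteria by reference. It prints no thresholds for CR, CRi, PR or MLFS either, so it plainly relies on cited sources, and silence on duration need not mean that none is required. This stands in part. A reader might infer that the plan lets one isolated blood value make a responder; no passage says so, and the cited source, not available here, may supply the missing conditions for the count lineages. But having chosen to print HI criteria, the protocol prints them without those conditions and expressly accepts blood-only blast response.

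Second, the benchmark also lists HI. Section 11.2 gives the 10% for CR/CRp/CRi/PR/HI/MLFS, from the same institution, so some supportive-care responses may already be inside it. This also stands in part, and it is why the tabulated figures are upper-end. It does not dispose of the point. The historical list is qualified by a blast reduction above 50%, whereas here an erythroid, platelet or neutrophil improvement alone counts. Section 3.0 states the 30% target on CR/CRi/PR without HI.

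Third, Section 11.2 treats patients who drop out before completing all cycles as failures in the primary analysis. Read literally, that would remove some spurious responders from the final ORR. It is not stated to apply to the interim counts behind Table 8.

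Three further inferences go too far. The futility rule is not disabled: at q = 10% it still stops with probability 0.56. The documents do not show that nearly all patients receive transfusion or growth factors; they report entry cytopenias, not treatment rates. Nor is supportive-care use unrecoverable: hydroxyurea is on the CRF, and the rest can be sought in the medical record.

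**Conclusion.** The point holds in this form: the printed HI rule can count effects of transfusion, growth factor or hydroxyurea as primary responses, and the same miscount feeds the futility looks. The exposure is clearest for peripheral blast reduction during hydroxyurea. For the count lineages it depends on whether the cited criteria carry conditions that the protocol does not print.

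The direction is toward a higher ORR and less frequent stopping; the amount cannot be determined from the documents. Under an assumed q of 5% to 20% and a true ORR of 10%, the loss in stopping probability runs from 0.93 − 0.76 = 0.17 to 0.93 − 0.24 = 0.69, before any cancellation through the benchmark. Even the low end is a material loss for a rule that is the trial's main protection against continuing an inactive regimen.

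**What to change.** These changes govern how response is counted, not how patients are treated.

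1. In Section 8.0, count erythroid, platelet and neutrophil HI only on a confirmed value not affected by recent transfusion or growth factor for that lineage. The sponsor should set the windows in line with the cited criteria and state a rule for patients already transfused at baseline.
2. Count blast response on marrow, or on blood only when no recent hydroxyurea was given, with the sponsor defining recent.
3. In Sections 5.6 and 7.2.6, add transfusion and growth-factor dates to the CRF, taken from the existing medical record.
4. In the analysis plan, report ORR without HI as a sensitivity analysis.
5. State whether the 10% benchmark counted HI under the same rules, and reconcile the response lists in Sections 3.0 and 11.2. Without this, tightening HI on the trial side alone could tilt the comparison the other way.

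The cost is a wording amendment and one CRF page. The counts already scheduled twice weekly in the first three cycles can serve for confirmation, so no extra visits or tests are needed. The downside is a somewhat lower ORR and some patients who cannot be assessed for a given HI lineage.

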8.1 Discontinuation Criteria for Individual Patients

9.1.1 Patient Withdrawal

Patients may voluntarily withdraw consent to participate in the clinical study at any time and without giving any reason. Their withdrawal will not jeopardize their relationship with their healthcare providers or affect their future care. Patients may also choose to withdraw from study treatment, but agree to remain in the study for follow-up procedures.

9.1.2 Investigator Discontinuation of Patient

The investigator may exercise medical judgment to discontinue study treatment if clinically significant changes in clinical status or laboratory values are noted.

9.1.3 Criteria for Protocol-Defined Required Discontinuation of Treatment

The protocol requires discontinuation of study treatment for the following reasons:

1. Patient requests discontinuation.
2. Unacceptable toxicity that in the opinion of the investigator makes it unsafe to continue therapy.
3. Clinically significant progressive disease.
4. Investigator discretion.

9.1.4 Follow-Up at Treatment Discontinuation or Early Withdrawal

Patients who discontinue treatment for any reason should complete end-of-treatment procedures when possible. End of treatment procedures will include a physical examination, CBC with differential and platelets and a limited chemistry profile (total bilirubin, serum creatinine, SGPT or SGOT). A bone marrow aspiration may be recommended only if non-response or progressive disease cannot be unequivocally diagnosed from peripheral blood. Although treatment will be discontinued at that time, all patients who do not withdraw consent for follow-up, die, or become lost to follow-up, will remain on study for follow-up evaluations. Subject will be followed for toxicity for at least 30 days after the last protocol treatment. The 30-day follow-up visit (+ or – 3 days) will be scheduled as a clinic visits for clinical evaluation and physical examinations. [The Subject will then be followed every 3-6 months for up to 5 years after the last dose of study drug.](#) If the patient cannot make it to the MDACC clinic for this visit, the required follow up treatment procedures may be done with a local physician and the records forwarded to MDACC. The research nurse will contact the patient by telephone and get a verbal assessment of the patient's condition. The phone conversation will then be documented in the patient's charts.

9.2 Study Stopping Rules

The principal investigator and MDACC IND office have the right to terminate this clinical study at any time. The principal investigator and MDACC IND office, as appropriate, will be involved in any decisions regarding terminating the study, temporarily suspending enrollment, or stopping ongoing treatment with study treatment.

Reasons for terminating the clinical study or a study site's participation include, but

are not limited to, the following:

- The incidence or severity of an adverse reaction related to treatment in this study or other studies indicates a potential health hazard to patients
- Data recording is significantly inaccurate or incomplete
- Study site personnel are noncompliant with study procedures
- Pattern of noncompliance is observed

9.3 Protocol Violations and Deviations

Protocol violations are defined as significant departures from protocol-required processes or procedures that affect patient safety or benefit potential, or confound assessments of safety or clinical activity. A protocol deviation is a departure from the protocol that does not meet the above criteria. Protocol violations or deviations may be grouped into the following classes:

- Enrollment criteria
- Study activities (missed evaluations or visits) except for those allowed per protocol
- Noncompliance with dose or schedule, including dose calculation, administration, interruption, reduction, or delay; or discontinuation criteria
- Investigational product handling, including storage and accountability
- Informed consent and ethical issues

9 ADVERSE EVENT REPORTING

- 9.1** Adverse event is any untoward medical occurrence that may present during treatment with a pharmaceutical product but which does not necessarily have a causal relationship with this treatment.

Adverse drug reaction is a response to a drug which is noxious and unintended and which occurs at doses normally used in man for prophylaxis, diagnosis, or therapy of disease or for the modification of physiologic function.

Assessing causal connections between agents and disease is fundamental to the understanding of adverse drug reactions. In general, a drug may be considered a contributory cause of an adverse event if, had the drug not been administered, 1) the event would not have happened at all, 2) the event would have occurred later than it actually did, or 3) the event would have been less severe.

The Investigator or physician designee is responsible for verifying and providing source documentation for all adverse events and assigning the attribution for each event for all subjects enrolled on the trial.

- 9.2 Serious Adverse Event Reporting (SAE)**

An adverse event or suspected adverse reaction is considered “serious” if, in the view of either the investigator or the sponsor, it results in any of the following outcomes:

- Death
- A life-threatening adverse drug experience – any adverse experience that places the patient, in the view of the initial reporter, at immediate risk of death from the adverse experience as it occurred. It does not include an adverse experience that, had it occurred in a more severe form, might have caused death.
- Inpatient hospitalization or prolongation of existing hospitalization
- A persistent or significant incapacity or substantial disruption of the ability to conduct normal life functions.
- A congenital anomaly/birth defect.

Important medical events that may not result in death, be life-threatening, or require hospitalization may be considered a serious adverse drug experience when, based upon appropriate medical judgment, they may jeopardize the patient or subject and may require medical or surgical intervention to prevent one of the outcomes listed in this definition. Examples of such medical events include allergic bronchospasm requiring intensive treatment in an emergency room or at home, blood dyscrasias or convulsions that do not result in inpatient hospitalization, or the development of drug dependency or drug abuse (21 CFR 312.32).

- Important medical events as defined above, may also be considered serious adverse events. Any important medical event can and should be reported as an SAE if deemed appropriate by the Principal Investigator or the IND Office.
- All events occurring during the conduct of a protocol and meeting the definition of a SAE must be reported to the IRB in accordance with the timeframes and procedures outlined in “The University of Texas M. D. Anderson Cancer Center Institutional Review Board Policy for Investigators on Reporting Unanticipated Adverse Events for Drugs and Devices”. Unless stated otherwise in the protocol, all SAEs, expected or unexpected, must be reported to the IND Office, regardless of attribution (within 5 working days of knowledge of the event).
- **All life-threatening or fatal events**, that are unexpected, and related to the study drug, must have a written report submitted within **24**

hours (next working day) of knowledge of the event to the Safety Project Manager in the IND Office.

- Unless otherwise noted, the electronic SAE application (eSAE) will be utilized for safety reporting to the IND Office and MDACC IRB.
- Serious adverse events will be captured from the time of the first protocol-specific intervention, until 30 days after the last dose of drug, unless the participant withdraws consent. Serious adverse events must be followed until clinical recovery is complete and laboratory tests have returned to baseline, progression of the event has stabilized, or there has been acceptable resolution of the event.
- Additionally, any serious adverse events that occur after the 30 day time period that are related to the study treatment must be reported to the IND Office. This may include the development of a secondary malignancy.

Reporting to FDA:

- Serious adverse events will be forwarded to FDA by the IND Sponsor (Safety Project Manager IND Office) according to 21 CFR 312.32.

It is the responsibility of the PI and the research team to ensure serious adverse events are reported according to the Code of Federal Regulations, Good Clinical Practices, the protocol guidelines, the IND Office guidelines, and Institutional Review Board policy

